## **1. Background and Rationale**

### **PROTOCOL SUMMARY**

HIV-related disparities in diagnosis and disease outcomes persist among Latinos, and Latinos living with HIV show a lower percentage of viral suppression compared to the general HIV-positive population. A growing body of work suggests that stigma and discrimination contribute to health disparities, especially among people living with HIV, who may experience discrimination due to multiple stigmatized identities related to HIV-serostatus, race/ethnicity, and sexual orientation. Internalized stigma and discrimination may lead to health-related disparities by increasing detrimental physiological stress responses, resulting in maladaptive coping and poor health behaviors, including non-adherence to treatment. Moreover, the chronic stress of discrimination may weaken immune function, leading to worse HIV outcomes, including increased HIV viral load.

In the proposed research, we will integrate adherence skills-building strategies into a recently developed intervention, Siempre Seguiré, a 7-session group cognitive behavioral therapy (CBT) intervention for HIV-positive Latino men who have sex with men (LMSM) that aims to improve adaptive coping responses to discrimination. We hypothesize that the intervention will improve coping responses to discrimination and HIV treatment adherence.

### **2. Objectives**

This objectives of this study are: (1) to modify and refine Siempre Seguiré, a newly developed culturally congruent CBT group intervention for HIV-positive LMSM, to include strategies for antiretroviral treatment adherence and retention in HIV care; and (2) to conduct a small randomized pilot of Siempre Seguiré to examine feasibility and acceptability, as well as to explore preliminary effects on: (a) coping responses to discrimination; and (b) antiretroviral treatment adherence, viral load suppression, and HIV care retention, among LMSM living with HIV.

### **3. Study Design**

This randomized controlled trial builds on a pilot trial of the Siempre Seguiré intervention. We will conduct 4 intervention groups and 4 wait-list control groups of 15 participants each (n=120). After participants complete the baseline assessment, we will randomize them into the intervention and wait-list control groups. We will provide the program to any interested control participants shortly after the 6-month follow-up surveys are completed. Our proposed sample size (60/condition) is consistent with those recommended for small intervention tests in staged intervention development.

### **4. Methods**

#### *Screening/Recruitment*

As in our prior pilot test, we will recruit participants via fliers left at the clinic at which the intervention will be conducted (Bienestar) and other AIDS service organizations (ASOs) (in waiting areas, on bulletin boards), fliers disseminated by Bienestar staff (e.g., case managers) to clients, and online advertisements. We will hold brief information sessions at client and staff gatherings. We will hire a

research assistant from the local community for recruitment and tracking who is well-connected with the local HIV population and familiar with local HIV services for Latinos.

Participants will be eligible if they are  $\geq 18$  years-old, are HIV-positive (verified by medication bottles or copies of laboratory results), were biologically male at birth and identify as male, identify as Latino, and report having sex with men in the past 12 months. To maximize chances of showing effects, participants must also either be not on antiretroviral treatment (ART) OR not fully engaged in care (i.e., less than 2 visits in the past 12 months) and/or missed at least 1 ART dose in the past month. Transgender women will not be included because they face discrimination regarding gender identity, which would necessitate a differently tailored intervention.

### *Procedures*

The **Siempre Seguiré intervention** will be conducted in groups and situated in a trusted community venue. The intervention was developed with, and will be delivered by, credible community stakeholders knowledgeable about LMSM culture—individuals not viewed as authority figures or part of the medical system. The intervention will be led by an expert facilitator (with experience leading groups) and a peer co-facilitator (with experience working with HIV-positive LMSM). Both facilitators are matched on client ethnicity to increase credibility and trust.

The intervention will utilize several unique counseling techniques.

*Psychoeducation:* All participants will receive basic HIV and adherence education. We will raise awareness about disparities and discrimination (e.g., links between discrimination and nonadherence) and address mistrust. Facilitators will acknowledge historical and current challenges, including discrimination, which lead to mistrust, and mental health, substance use, and poverty (and, if necessary, provide referrals for services). The intervention will also address HIV and sexual orientation stigma in Latino communities, and how stigma can be a barrier to seeking support, accessing healthcare, and adherence.

*Cognitive Behavioral Therapy (CBT):* CBT, one of the most widely used and well-supported treatment approaches for improving mental health and health behaviors, including ART adherence, is well-suited as a change strategy for MSM and people of color. CBT aims to empower clients to be their own agents of change, building on existing strengths and skills. CBT involves educating clients about the relations among their thoughts, behaviors, and emotions. Counselors help clients to understand a given problem behavior (e.g., rumination after discrimination; nonadherence) in terms of the chain of events that led to the behavior (a functional analysis/chain analysis) as well as the behavior's consequences. Clients can be guided through a step-by-step, micro-level recounting of thoughts, feelings, and emotions related to a specific event/behavior chain (distal vulnerability factors, proximal prompting events, immediate and longer-term consequences of coping strategies), and they work with the counselor collaboratively to identify problematic 'links' in the chain. Counselors teach clients cognitive and behavioral skills (mindfulness, cognitive restructuring, relaxation) for better coping. Skills are practiced in session, and behavioral self-monitoring and further practice are assigned between sessions to facilitate skills generalization. The counselor teaches clients the utility of having a 'toolbox' of potential strategies to use for different situations, and how to strategically select a skill that best matches a given problem. Skills are understood and evaluated in the context of clients' values ("It's important to stay healthy") and goals ("I want to take all of my medications"). CBT is useful in groups because antecedents or

consequences of many problem behaviors are interpersonal (e.g., disrupted relationships) and because clients can 'test out' new skills vicariously through the experiences of other group members.

We will use similar **participant surveys** to those in the pilot, which we found to be feasible (and not overly burdensome) for participants to complete in about 90 minutes as well as psychometrically sound (as evidenced by the internal consistency reliabilities presented below). We will administer 3 survey waves [baseline, 1-week post-intervention (~4-months post-baseline), 6-months post-baseline]. Surveys will be administered at Bienestar using audio computer-assisted self-interviews. Participants will complete the baseline survey before randomization. Participants who drop out of the program will be encouraged to complete all surveys.

To validate self-reports, we will obtain HIPAA consent for appointment attendance in the last year from **medical records**, from which we will examine whether the participant had at least one HIV medical care visit in each 6-month period over the last 12 months, with a minimum of 60 days between visits. Participants will list all prescribed ART medications using medication bottles (brought to the interview). Adherence will be measured continuously and electronically from baseline to 6-month follow-up with the **Medication Event Monitoring System (MEMS)**. At baseline (~2 months prior to the first intervention session, to allow time for any reactance to the MEMS assessment to decrease prior to the intervention), interviewers will assist clients with dispensing the medication with the most complex dosing schedule or the base medication of the regimen if all medications have the same schedule (e.g., non-nucleoside reverse transcriptase inhibitor, protease inhibitor, integrase inhibitor), into a MEMS bottle. Monthly from 2-6-months post-baseline, interviewers will download adherence data and participants will report instances in which the cap was not used as intended in the past 2 weeks (how often the bottle was opened without removing a dose, a dose was taken from a source other than the bottle, such as a pillbox, and whether multiple doses were removed at a time and "pocketed" for later ingestion). Data for the past two weeks at each time-point will be adjusted using these responses for a more valid assessment. MEMS software calculates the percentage of total scheduled doses actually taken, which will be dichotomized at  $\geq 85\%$  of doses taken at each time-point, following research suggesting that moderate adherence has clinically significant effects. We will assess self-reported adherence using items validated against viral load and pill counts: number of doses missed last week; percentage of prescribed medications taken last month (on a visual analogue scale), and ability to take all medications as prescribed in the past 4 weeks. We will obtain HIPAA consent to extract the last two viral load values from medical records. Viral load suppression will be defined as  $< 200$  copies of virus per milliliter of blood plasma.

For **process evaluation** purposes, we will record number of intervention sessions attended per participant, and participants will complete a brief survey after each session on facilitator clarity, preparedness, and likeability, and utility of session content. Facilitators and a research team observer will complete post-session evaluation forms to assess session flow, areas for improvement, and whether key elements and activities were covered adequately; this will allow us to assess whether some activities need to be shortened or eliminated. After the last session, we will conduct 60-minute qualitative debriefing exit interviews with intervention participants, which will be transcribed and translated. Topics will include general reactions to the program (content, format, logistics), and reasons for any intervention non-participation or discontinuation. We will elicit suggestions for improvement (e.g., what topics to add). We will develop a codebook listing key themes related to program feedback and suggestions for improvement. Using *Dedoose* (a qualitative data management program), two coders will mark text areas with each code. We will measure coder consistency in 20% of participants' responses,

aiming for  $\kappa \geq .70$ . Following coding, study PIs will examine all coded passages and compile a list of key intervention feedback.

## 5. Statistical Analysis

Consistent with R34 guidelines, our primary purposes are to develop the intervention and collect preliminary data regarding feasibility and acceptability; conducting formal statistical tests of outcomes or attempting to obtain a measure of effect size is not justified with a limited sample size. Thus, the proposed analyses are meant to be exploratory, to aid in planning for a full RCT. We do not expect to have sufficient statistical power to adequately examine program effects in multivariate models. However, we will explore bivariate effects in the proposed analyses, and will also examine use of a small set of covariates.

We will explore whether the program improves coping responses to discrimination; reduces medical mistrust, distress, and internalized stigma; improves adherence and retention in care; and increases rates of viral suppression in the intervention vs. control group. We will use generalized linear mixed models, i.e., a repeated-measures linear regression approach to predict coping with data collected at baseline and 4- and 6-month follow-up that compares differences between intervention and control means over time. We will employ a parallel repeated-measures logistic regression approach to predict optimal adherence (i.e., dichotomous adherence,  $\geq 85\%$  of doses taken) with electronic monitoring data collected at baseline and 2, 4, and 6-month follow-up. We will conduct logistic regressions predicting viral load (dichotomized as suppressed vs. not suppressed) at 6-months post-baseline with dichotomized baseline viral load. We will use similar repeated-measures linear models to examine intervention effects on the other secondary outcomes, as well as on linear adherence (percentage of prescribed doses taken) and log viral load change from baseline. We will select covariates from variables that are hypothesized on the basis of theory and previous research to predict outcome variables (see Fig. 1), and for which we find support for hypotheses in bivariate baseline analyses. We will use intention-to-treat analysis, i.e., we will analyze participants according to the condition to which they were randomized, regardless of their subsequent session attendance. We will account for all participants who responded to the baseline survey, regardless of follow-up survey or item completion, using nonresponse weighting or multiple imputation, as appropriate. Because each participant will complete the baseline survey prior to randomization, we will compare follow-up survey respondents with nonrespondents on demographics and medical variables. If we have high survey participation and find significant differences between respondents and nonrespondents, we will use inverse predicted probability nonresponse weights (and use linearization to correct estimated standard errors if there are modest deviations from standard statistical inference assumptions). We will address item nonresponse through multiple imputation.

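### The program is delivered in four therapy groups of 15, but no outcome model has a therapy-group term, so standard errors at 4 and 6 months are too small if outcomes correlate within groups

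*Combined protocol and SAP*

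**What the plan says.** Section 3 (Study Design) states: "We will conduct 4 intervention groups and 4 wait-list control groups of 15 participants each (n=120"). Individuals are randomized after the baseline assessment, 60 per condition. On the control arm it says: "We will provide the program to any interested control participants shortly after the 6-month follow-up surveys are completed".

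Section 4 (Procedures) says that the intervention "will be conducted in groups and situated in a trusted community venue", led by a facilitator and a peer co-facilitator. One reason given for the group format is that clients can try out "new skills vicariously through the experiences of other group members". Baseline falls about "2 months prior to the first intervention session".

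Section 5 (Statistical Analysis) specifies these outcome models:

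- **Coping:** generalized linear mixed models, spelled out as "a repeated-measures linear regression approach to predict coping with data collected at baseline and 4- and 6-month follow-up".
- **Electronically monitored adherence (85% or more of doses):** a parallel repeated-measures logistic model.
- **Viral suppression:** a logistic regression at 6 months with dichotomized baseline viral load.
- **Other secondary outcomes, percentage adherence and log viral load change:** similar repeated-measures linear models.

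None of these names therapy group, facilitator or cohort. The section also says that "conducting formal statistical tests of outcomes or attempting to obtain a measure of effect size is not justified with a limited sample size" and that "the proposed analyses are meant to be exploratory, to aid in planning for a full RCT".

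**The concern.** Members of a therapy group share sessions and each other, and the protocol expects them to influence one another. Their outcomes after the sessions may therefore be correlated. Controls receive no program until after the 6-month surveys, so on the documents' description the 4- and 6-month comparisons are partially nested: grouped in one arm, individual in the other.

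A mixed model could hold a group effect. Section 5, however, defines its mixed models as repeated-measures models, which handle correlation within a person and not between members of a group. The viral suppression model uses one time point and handles no correlation. The linearization remark is conditional, belongs to the nonresponse weighting, and names no cluster.

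No confirmatory conclusion is at stake. What is at stake is the apparent precision of the arm comparisons that the plan will still fit and use in planning the full trial. The mechanism is clearest for coping. For adherence, retention and viral load, the size of any correlation is unknown. The 2-month adherence point is not affected, because it falls at about the time of the first session.

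**Working it through.** **Inputs from the documents.** 4 groups × 15 = 60 per condition and 8 × 15 = 120 in total, which reproduces the stated sample size (section 3). The documents give no power calculation, interval width or ICC.

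**Assumptions.** The ICC in the intervention arm is 0.01, 0.02, 0.05 or 0.10. Controls are independent, variances are equal, all 15 per group are analyzed, and there is one follow-up time.

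**Formulas.**

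- Design effect in the intervention arm: DE = 1 + (15 − 1) × ICC.
- Effective sample size of that arm: 60 / DE.
- Ratio of true to reported standard error of the arm difference: √((DE + 1)/2).
- Actual error of a nominal 95% interval: 2 × (1 − Φ(1.96 / ratio)).

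For ICC 0.05: DE = 1 + 14 × 0.05 = 1.70. Effective n = 60/1.70 = 35. Ratio = √(2.70/2) = 1.16. Error = 2 × (1 − Φ(1.96/1.162)) = 9.2%.

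| Assumed ICC | DE | Effective n of 60 | SE ratio | Coverage | Error by formula | Error, simulated |
|---|---|---|---|---|---|---|
| 0.01 | 1.14 | 53 | 1.03 | 94.2% | 5.8% | 5.8% |
| 0.02 | 1.28 | 47 | 1.07 | 93.4% | 6.6% | 6.5% |
| 0.05 | 1.70 | 35 | 1.16 | 90.8% | 9.2% | 9.2% |
| 0.10 | 2.40 | 25 | 1.30 | 86.7% | 13.3% | 13.4% |

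The simulated column comes from 40,000 trials per ICC: a normal outcome, 4 groups of 15 against 60 independent controls, analyzed without regard to group.

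**Binary outcome.** For a logistic model of 6-month suppression, with an assumed 50% or 70% suppressed, the simulated error is 5.5–6.1%, 6.5–7.3%, 8.8–10.0% and 12.9–14.2% at the four ICCs.

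**Sensitivity to the structure.**

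- *Ten analyzed per group:* the ratio is 1.02, 1.04, 1.11 and 1.20, and the error 5.5%, 6.0%, 7.7% and 10.4%.
- *Wait-list groups equally clustered (15 per group):* the ratio becomes √DE = 1.07, 1.13, 1.30 and 1.55.

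**Does a group-level analysis repair it?** Taking the intervention-arm variance from the four group means, with Satterthwaite degrees of freedom, gives simulated error of 5.5%, 5.4%, 5.6% and 6.0%. For the binary outcome, a group-level summary gives 5.3% to 6.8%.

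**How well can four groups estimate the ICC?** The one-way ANOVA has F(3, 56). The chance of an ICC estimate at or below zero is 54%, 48%, 36% and 23% at the four true values. If the estimate is 0.05, then F = (1 + 14 × 0.05)/(1 − 0.05) = 1.79, and the exact 95% interval for the ICC is −0.03 to 0.62.

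**The case against.** The strongest reply is that little depends on these models. The plan disclaims formal tests and effect-size estimation, puts feasibility and acceptability first, and never promises confidence intervals. This stands as a limit on the consequence. But the plan still fits intervention-versus-control models, those models yield standard errors, and the plan says the analyses will help design the next trial.

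Second, the size rests on assumed ICCs. This stands too. At 0.02 or less, coverage is still above 93%, and correcting for groups changes the error by only about one percentage point or less. Dropout would shrink the effect further, as the ten-per-group figures show. Retention is judged over 12 months, much of it before any session, so its exposure to group effects is limited.

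Third, parts of the structure are uncertain. If one facilitator pair leads all four groups, facilitators add no variance between groups; shared sessions and members still can. The text also speaks of wait-list groups. If these interacted before 6 months the problem would be larger, but the documents describe no program contact for them in that period.

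Fourth, section 5 does not forbid a group effect. That is true, but an analyst who follows it as written would not include one. Finally, the simulations cover single-follow-up and group-level analyses, not the full repeated-measures or logistic models with a group effect. They show the direction and approximate size of the correction, not the exact performance of those models.

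**Conclusion.** The concern holds. The documents describe individual randomization with delivery in four interacting groups, and no outcome model accounts for group. Whenever the within-group correlation is positive, the reported standard errors for the 4- and 6-month comparisons are too small.

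The omission is certain; its size is not. Under the stated assumptions the understatement is slight at an ICC of 0.02 or less and material at 0.05 to 0.10, where the actual error is 9.2% to 13.3% with 15 analyzed per group, or 7.7% to 10.4% with 10. Because the analyses are exploratory, this should be fixed but does not threaten a confirmatory claim.

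**What to change.** - Record each intervention participant's therapy-group number.
- For outcomes measured after the sessions, add a therapy-group random effect in the intervention arm, with wait-list controls as singletons (a partially nested model). Use Satterthwaite or Kenward-Roger degrees of freedom for the linear outcomes.
- For the logistic outcomes (adherence of 85% or more, viral suppression), include the same group effect with a small-sample t reference, or use a group-level summary analysis.
- Report the between-group variance or ICC with its interval. State that four groups estimate it very imprecisely, so it should not alone set the ICC for the full RCT.

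The change needs analysis wording and one recorded variable. Randomization, sample size and visits are unaffected. The price is wider intervals on few degrees of freedom. In simulation of the group-mean analysis, the median 95% half-width rises from 0.36 SD when groups are ignored to 0.39, 0.40, 0.45 and 0.52 SD at ICC 0.01, 0.02, 0.05 and 0.10, with median degrees of freedom of about 12, 11, 9 and 7.

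### The linear models for survey outcomes state neither a common baseline mean nor baseline adjustment; on the natural reading the arm comparison is unbiased but somewhat less precise than it could be

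*Combined protocol and SAP*

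**What the plan says.** Section 5 (Statistical Analysis) plans a repeated-measures linear model for coping "with data collected at baseline and 4- and 6-month follow-up that compares differences between intervention and control means over time". It extends the approach: "We will use similar repeated-measures linear models to examine intervention effects on the other secondary outcomes". Baseline is therefore a response wave alongside months 4 and 6. The section does not say that the arms share a baseline mean. Its covariate rule draws on theory and bivariate baseline analyses, and does not name the outcome's own baseline value. For dichotomised viral load, by contrast, the same section names both the time point (6 months) and the baseline value in the model.

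Section 4 (Procedures) fixes the timing of the survey: "Participants will complete the baseline survey before randomization". Section 3 (Study Design) sets the size: "4 intervention groups and 4 wait-list control groups of 15 participants each", 120 in all.

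Section 5 also limits what the outcome analyses are for: "conducting formal statistical tests of outcomes or attempting to obtain a measure of effect size is not justified with a limited sample size", and "the proposed analyses are meant to be exploratory, to aid in planning for a full RCT".

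**The concern.** When baseline is a response and each arm has its own baseline mean, the model estimates two quantities that randomisation makes equal in expectation. The chance baseline difference then enters the change contrast in full, although only part of it (the fraction r) predicts follow-up. A common baseline mean, or adjustment for the baseline value, removes that excess noise. Either is valid by design for the survey outcomes, because the survey is completed before allocation.

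What is at stake is efficiency in a trial of fixed, small size. The plan still compares the arms on coping, mistrust, distress and stigma to help plan a larger trial, and a sharper description would cost nothing in data.

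**Working it through.** **Inputs from the documents.** 4 × 15 + 4 × 15 = 120, or 60 per arm, which reproduces the stated total. There are three survey waves, with baseline before randomisation. There are four intervention groups. Control participants are offered the program only after the 6-month surveys, so group effects before then are placed in the intervention arm only. The documents give no power-based figure to reproduce.

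**Assumed, not in the documents.**
- Outcome SD of 1 at each wave.
- Correlation r between baseline and follow-up of 0.3, 0.5, 0.7 or 0.8.
- 20% dropout, missing at random, so m = 48 of n = 60 per arm are followed up.
- Post-baseline group variance of 0.05 SD², which adds g = 0.05/4 = 0.0125 to the variance of the arm difference.

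**Formulas for one follow-up visit.**
- Common baseline mean, or baseline adjusted: A = 2(1 − r²)/m + g
- Separate baseline means, difference in change: C = 2[(1 − r²)/m + (1 − r)²/n] + g

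**Best case (m = n = 60, g = 0).** A/C = (1 − r²)/[(1 − r²) + (1 − r)²] = (1 + r)/2.

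| r | A/C | Per-arm n at which the change contrast matches 60 |
|---|---|---|
| 0.3 | 0.65 | 60/0.65 = 92 |
| 0.5 | 0.75 | 60/0.75 = 80 |
| 0.7 | 0.85 | 60/0.85 = 71 |
| 0.8 | 0.90 | 60/0.90 = 67 |

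A three-wave generalised least squares calculation at r = 0.5 with 60 per arm gives standard errors at month 6 of 0.158 (common mean) and 0.183 (change). (0.158/0.183)² = 0.75, as the formula says.

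**With dropout and group variance (m = 48, g = 0.0125).** At r = 0.5, A = 2 × 0.75/48 + 0.0125 = 0.04375 and C = 0.04375 + 2 × 0.25/60 = 0.05208. The ratio is 0.84, and 1 − √0.84 = 8%.

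| r | A | C | A/C | Interval narrower by 1 − √(A/C) |
|---|---|---|---|---|
| 0.3 | 0.05042 | 0.06675 | 0.76 | 13% |
| 0.5 | 0.04375 | 0.05208 | 0.84 | 8% |
| 0.7 | 0.03375 | 0.03675 | 0.92 | 4% |
| 0.8 | 0.02750 | 0.02883 | 0.95 | 2% |

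A simulation of 20,000 runs under these assumptions gave A/C = 0.75, 0.84, 0.93 and 0.96.

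**Small-sample check.** With only four intervention groups, a normal quantile is too generous. A Satterthwaite approximation (3 df for the intervention arm, 47 for control) gives roughly 6 to 8 df, and the gains become about 12%, 7%, 3% and 2%. The direction and order of size hold. Absolute interval widths depend heavily on the assumed group variance and these few degrees of freedom, so none is given here.

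**The case against.** The strongest reply is that nothing in the plan turns on this. Section 5 makes feasibility and acceptability the primary purpose, disclaims formal tests and effect-size estimation, and expects too little power for multivariate models. Both models are unbiased, and intervals a few percent narrower change no decision. This stands as to priority. It does not remove the arm comparison that Section 5 goes on to plan, and the better model uses the same data.

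A second reply is that the wording does not exclude a common baseline mean or baseline adjustment. That also stands. If either is intended, nothing is lost and only the sentence is missing.

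A reader might infer more than the documents support:
- **A larger gain.** Against a plain arm difference at a visit with separate baseline means, intervals under the same assumptions would be 18% and 25% narrower at r = 0.7 and 0.8. But Section 5 compares means over time and does not point to that contrast, so those figures should not be used.
- **Bias.** Under randomisation the change contrast is unbiased.
- **A diluted effect.** An arm effect averaged over all three waves would shrink a constant follow-up effect to two thirds. The text does not describe such a contrast.
- **Other outcomes.** Section 5 also analyses "log viral load change from baseline", but Procedures only says it will "extract the last two viral load values from medical records", without showing that the baseline value predates randomisation. Nor is the baseline window for electronically monitored adherence shown to precede randomisation. The point does not extend to either, and the figures do not apply to the logistic adherence model.

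**Conclusion.** The point holds as a low-priority improvement in efficiency for coping and the other linear survey outcomes. Validity is not in question and no stated figure becomes wrong. Relative to the difference in change, the common-mean or adjusted model has 0.65 to 0.90 of the variance in the best case. Under the assumed dropout and group variance, intervals are about 13% narrower at r = 0.3, falling to 2% at r = 0.8, and slightly less with small-sample degrees of freedom. The size depends on a correlation, a dropout rate and a group variance that the documents do not give. The gain is zero if a common baseline mean or baseline adjustment is already intended.

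**What to change.** Add one or two sentences to Section 5:
- The linear models for survey outcomes use one common baseline mean for both arms, with separate arm means at months 4 and 6. Alternatively, they adjust for the outcome's baseline value, with the planned imputation or weighting.
- The arm differences at months 4 and 6 are the exploratory contrasts, and any interval around them is descriptive.

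No new data are needed. The common-mean model keeps participants who have only a baseline survey. The adjusted model drops them unless they are imputed or weighted, which Section 5 already provides for. If either approach is already intended, the change is wording only.

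### The logistic adherence model leaves out the month-3 and month-5 MEMS windows, which are collected and corrected, and gives no reason

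*Combined protocol and SAP*

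**What the plan says.** On collection, Procedures states: "Adherence will be measured continuously and electronically from baseline to 6-month follow-up". The download schedule is: "Monthly from 2-6-months post-baseline, interviewers will download adherence data". At the same visits participants report departures from intended cap use, and "Data for the past two weeks at each time-point will be adjusted using these responses for a more valid assessment".

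On timing, the MEMS bottle is first filled "At baseline (~2 months prior to the first intervention session", so the month-2 window falls at about the start of the sessions. The second survey is placed at "1-week post-intervention (~4-months post-baseline", so the program ends at about month 4.

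On analysis, section 5 fits a repeated-measures logistic model to "electronic monitoring data collected at baseline and 2, 4, and 6-month follow-up". It adds similar linear models for the secondary outcomes, "as well as on linear adherence (percentage of prescribed doses taken", and gives no time points for that measure.

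**The concern.** The collection plan produces five corrected windows after baseline, and the named model takes three of them. No reason is given for dropping the other two, although the visit, the download and the misuse report have already been spent on them.

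Month 5 matters most. If the month-4 download falls on the day of the one-week post-program survey, its two-week window begins about a week before the last session. Months 5 and 6 are then the only windows that lie wholly after the program, and the model uses one of them.

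Two things are at stake. Adherence is a named objective in a trial that says it does not expect enough power for multivariate models, so usable data should not be left aside without a reason. And because months 3 and 5 have no assigned role and the linear model has no stated time points, the windows could be chosen after the results are known.

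**Working it through.** The plan gives no precision, power or within-person correlation for adherence, so it has no figure to reproduce. All correlations below are assumptions. The formulas are linear approximations to the logistic model, with complete data and unit variance per window.

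**Count of windows.** Collected and corrected: months 2, 3, 4, 5, 6 (five). Named in the logistic model: months 2, 4, 6 (three). Left out: months 3 and 5. If the two-week windows are what is analysed, that is 3 × 14 = 42 corrected days against 5 × 14 = 70. The model also lists baseline, but the bottle is only dispensed then, so what a baseline MEMS value covers is undefined.

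**Contrast examined.** The mean of months 4 and 6 against the mean of months 4, 5 and 6, each given month 2. Month 3 falls during the sessions and does not enter this contrast.

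**Equal correlation r.** The variance of the mean of k windows, given one earlier window, is (1 + (k − 1)r)/k − r².

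| r | k = 2 (4, 6) | k = 3 (4, 5, 6) | Variance falls | SE falls |
|---|---|---|---|---|
| 0.4 | 0.540 | 0.440 | 18.5% | 9.7% |
| 0.5 | 0.500 | 0.417 | 16.7% | 8.7% |
| 0.6 | 0.440 | 0.373 | 15.2% | 7.9% |
| 0.7 | 0.360 | 0.310 | 13.9% | 7.2% |

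These figures borrow strength from month 2. Without it the r² term drops out, and the reduction is 1 − [(1 + 2r)/3]/[(1 + r)/2]: 14.3%, 11.1%, 8.3% and 5.9% at the same values of r.

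**Decaying correlation, AR(1), monthly value r.** At r = 0.5, given month 2:
- Months 4 and 6: (1 + 0.25)/2 − [(0.25 + 0.0625)/2]² = 0.625 − 0.0244 = 0.6006.
- Months 4, 5 and 6: (3 + 2(0.5 + 0.5 + 0.25))/9 − [(0.25 + 0.125 + 0.0625)/3]² = 0.6111 − 0.0213 = 0.5898.
- Reduction: 1 − 0.5898/0.6006 = 1.8%.

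The same steps with a simple average give a reduction of 10.6% at r = 0.3. At 0.7 and 0.9 they give an increase of 2.2% and 2.8%, because month 5 lies between two windows already in use. With optimal weights, where the variance is 1/(1′R⁻¹1) and R is the covariance of the windows given month 2, the reduction is about 12%, 4%, 0.6% and 0% at r = 0.3, 0.5, 0.7 and 0.9.

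**Mixed structure.** Suppose 0.3 of the variance is a stable person effect, 0.4 decays at 0.5 per month and 0.3 is window-specific. Correlations at lags of 1, 2, 3 and 4 months are then 0.500, 0.400, 0.350 and 0.325.
- Months 4 and 6: 0.700 − 0.3625² = 0.5686.
- Months 4, 5 and 6: 5.8/9 − 0.3583² = 0.5160.
- Reduction: 9.2%.

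Shares of 0.3, 0.3 and 0.4, with decay at 0.7 per month, give 0.5558 and 0.4934, a reduction of 11.2%. The 8 to 12% band needs a window-specific share of about 0.3 to 0.4. With a share of 0.2 the gain is nearer 5 to 7%.

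**The case against.** The case against is substantial. Section 5 declares the analyses exploratory and says formal outcome testing is not justified at this size. Months 4 and 6 coincide with the survey waves, so a model on that grid is coherent. No stated figure or decision changes. If the contrast of interest were month 6 alone with complete data, further windows would add little or nothing. All of this stands, and it keeps the point modest.

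The linear model's silence on time points also stands: the omission of months 3 and 5 is certain only for the logistic model. Since monitoring is continuous and the period behind each percentage is not defined, it would be too strong to say that the data are thrown away.

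Three stronger readings are tempting, and the documents do not support them.
- *Leaving out two of five windows costs 17% of precision.* The 17% is a variance figure at r = 0.5 under equal correlation, comes from month 5 alone, and corresponds to about 9% in standard error.
- *With month 5, 120 participants act like 144* (120/(1 − 0.167)). This also assumes that all 120 have MEMS data, yet men not on ART are eligible. It treats the outcome as continuous, and it ignores variation between intervention groups, which extra windows do not reduce.
- *Month 2 is a baseline to adjust for.* Randomization follows the baseline assessment, about two months before the first session. Month 2 is therefore measured after randomization, in a wait-list design where participants can be expected to know their arm.

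None of this explains why months 3 and 5 are left out of the repeated-measures model.

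**Conclusion.** The point holds as a modest efficiency and specification gap. The collection schedule and the logistic model do not match, and no reason is given.

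Adding month 5 to the post-program contrast lowers the variance by somewhere between nothing and 19%: about 14 to 19% under equal correlation of 0.4 to 0.7, about 8 to 12% under mixed structures, and near zero under strong AR(1), where a simple average can be up to 3% worse. The equal-correlation and mixed figures assume that information from month 2 is used; without it they are smaller. The trial's own data will show which structure applies.

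One benefit does not depend on equal correlation. A participant who misses the month-4 or month-6 download can still contribute a corrected month-5 window, and section 5 itself plans for nonresponse. Five windows would also describe the adherence course and its correlation better for planning the full trial, which is the stated purpose of these analyses.

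**What to change.** In section 5:
- Enter all five monthly MEMS windows (2, 3, 4, 5, 6) in both the logistic and the linear repeated-measures adherence models, or give the reason for leaving any out.
- State the period that each window's percentage covers, and what the baseline MEMS value is, if there is one.
- Estimate the post-program arm contrast from months 4, 5 and 6 with model-based weights, under a correlation structure that can decay over time, rather than by a simple average. This treats the arm difference as roughly constant over those months, so report the month-by-month differences alongside it.
- Treat month 2 as a pre-session, post-randomization repeated measure, not as a baseline covariate.
- Name in advance a simpler correlation structure in case the logistic model does not converge.

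The cost is revised wording and slightly more modelling work. It needs no new visits, downloads or participant burden. The analyses remain exploratory and no stated figure changes.
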